1.2.2 MDMA

MDMA is a ring-substituted phenylisopropylamine derivative invented by the Merck pharmaceutical company in 1912 [26, 27]. Similar to SSRIs, MDMA binds to the serotonin transporter, but has additional effects on carrier-mediated release and reuptake inhibition of norepinephrine and to a lesser extent in humans, dopamine [28-34]. MDMA also increases levels of affiliative neurohormones oxytocin and vasopressin, which increases trust and attenuates reactivity to threatening cues, and some researchers have suggested a role for oxytocin in treating PTSD. The indirect effects of MDMA on central and peripheral neurohormone release contribute to a novel mechanism that may help regulate the HPA axis, which would treat the core psychopathology of PTSD for a durable remission.

Onset of MDMA effects occurs ~0.5 to 1 hour after oral administration, and peak effects occur 1.25 to 2 hours after the initial dose. Effects of the initial dose last 3 to 6 hours, with most effects returning to baseline or near-baseline levels 6 hours after final drug administration [35-37]. Orally administered doses of MDMA have a half-life of 7 to 9 hours in humans. Unlike approved PTSD medications, therapeutic effects of MDMA have a rapid-onset and do not require daily dosing or a steady state in the blood to be effective. Thus, the effects of MDMA are distinct from and go well beyond anxiolytics and SSRIs. Furthermore, there is no evidence that MDMA creates a physical dependency, as benzodiazepines do. Previous studies of polydrug users have found a small percentage of people exhibit problematic use of Ecstasy (material represented as containing MDMA) [38, 39]. Studies of regular or problematic Ecstasy users indicate that on average, regular use occurs no more often than once a week [40]. Hence, MDMA may have moderate abuse potential. See the Investigator's Brochure (IB) for a more detailed explanation.

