	Treatment Period 8 to 20 weeks Treatment 1 Treatment 2 Treatment 3													
		Tres	atment 1			Trea	tment 2				Study Termi- nation			
Visit	V4	V5	V6	V7	V8	V9	V10	V11	V12	V13	V14	V15	V16	
Visit Description	Exp. 1	Int. 1.1	Int. 1.2 F	Int. 1.3 ^F	Exp. 2	Int. 2.1	Int. 2.2 F	Int. 2.3 ^F	Exp. 3	Int. 3.1	Int. 3.2 ^F	Int. 3.3 ^F	Study Termination	
Visit Timing	1 to 14 days after V3	Morning after V4	10 to 18 days after V4	At least 2 days after V6; 1 to 14 days before V8	21 to 56 days after V4	Morning after V8	10 to 18 days after V8	At least 2 days after V10; 1 to 14 days before V12	21 to 56 days after V8	Morning after V12	10 to 18 days after V12	At least two days after V14	24 to 32 days after V12	
Past/Current Medication & Adherence	√	√	√	√	√	√	~	√	√	✓	√	~	✓	
Drug Screen	✓				✓				✓					
Pregnancy Screen	✓				✓				✓				✓	
All AEs A	✓	✓	✓	✓	✓	✓	✓	√	✓	✓	√	✓	✓	
Container Assignment ^B	√				✓				√					
Administer IMP	✓				✓				✓					
At least 6-hour Exp. Session	√				√				√					
BP, Pulse, Temperature	√ c	✓ H			√c	✓ H			√c	✓ H			✓ D	
Potential Overnight Stay	√				√				√					
90-min Integrative Session		√	√	√		√	√	√		√	√	√		
Phone Call Follow-up ^E		√				√				√				
Weight			-										√	
Measures (ePRO or Clinician- Administered ^G	√	✓ E	√	√	√	✓ E	√	· C.D. · Listois	√	✓ E	√ 1:11.:.	√	√	

All Adverse Events (AEs) includes collecting Serious Adverse Events, AEs of Special Interest, AEs of Psychiatric Status, AEs requiring medical advice or attention, AEs that indicate withdrawal of a participant, and all other AEs

^B Obtain container assignment 24 to 48 hours prior to each Experimental Session

^C During Experimental Sessions, vitals are measured within 15 minutes before Investigational Product administration, immediately before the supplemental dose is administered (or would be, if supplemental dose not given), and approximately 6 hours after initial dose, and as needed. Additional measurements to be taken if clinically indicated (e.g., if blood pressure does not return to baseline).

^D At Study Termination, only blood pressure needs to be measured

^E 14 days of phone call follow-up: every other day after the Experimental Session; includes C-SSRS administration and AE collection

F All Integrative Sessions must be at least 2 days apart

^G Refer to Table 6: Time and Events-Measures for details

^H If clinically indicated.

MAPPUSX Protocol Amendment 3 Version 1: 15 March 2023

Table 6: Time and Events-Study Measures

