7.3.1 Experimental Sessions

There will be three open-label Experimental Sessions (Visits 4, 8, 12). Procedures for MDMA-assisted therapy will remain the same across all sessions and all procedures regardless of dose received. Experimental Sessions must be at least 6 hours long, measured from 30 minutes prior to IMP administration. The Experimental Sessions will consist of:

- Experimental Session 1 (Visit 4) will occur 1 to 14 days after Preparatory Session 3 (Visit 3). The first Experimental Session will include 80 mg of MDMA followed by a supplemental half-dose 1.5 to 2 hours after the initial dose unless tolerability issues emerge with the first dose or it is refused by the participant.
- Experimental Session 2 (Visit 8) will occur 21 to 56 days after Experimental Session 1 (Visit 4) and 1 to 14 days after Integrative Session 1.3 (Visit 7). A dose of 80 or 120 mg MDMA will be administered. A supplemental dose (40 mg or 60 mg) will be administered 1.5 to 2 hours after the initial dose unless tolerability issues emerge with the first dose or it is refused by the participant. If the participant received an initial dose of 80 mg, a 40 mg supplemental dose will be used. If the participant received an initial dose of 120 mg, a 60 mg supplemental dose will be used. If drug supply does not permit availability of 60 mg capsules, a reduced supplemental dose of 40 mg may be administered following the 120 mg initial dose.
- Experimental Session 3 (Visit 12) will occur 21 to 56 days after the second Experimental Session (Visit 8) and 1 to 14 days after Integrative Session 2.3 (Visit 11). A dose of 80 or 120 mg MDMA will be administered. A supplemental dose (40 mg or 60 mg) will be administered 1.5 to 2 hours after the initial dose unless tolerability issues emerge with the first dose or it is refused by the participant. If the participant received an initial dose of 80 mg, a 40 mg supplemental dose will be used. If the participant received an initial dose of 120 mg, a 60 mg supplemental dose will be used. If drug supply does not permit availability of 60 mg capsules, a reduced supplemental dose of 40 mg may be administered following the 120 mg initial dose.

Table 7: Schedule of Procedures for Experimental Sessions

Approximate Time during an 8 hour session	Procedure or Action
9:30	Urine drug screen and pregnancy test, concomitant medication information
	collected, participant acclimated to environment, C-SSRS. Begin video
	recording.

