End of Experimental Session

- The therapy pair will administer Since Last Visit C-SSRS.
- The therapy pair will record AEs and concomitant medications.
- The session may be ended if all medical and psychiatric parameters are acceptable, elevations in vital signs have resolved to pre-IMP levels, the participant is alert, ambulatory, and emotionally stable.
- Participants with persistent elevations in blood pressure at the end of Experimental Sessions will
 have additional blood pressure assessments after the session and the next morning during the
 integration session. If deemed necessary, the blood pressure will be monitored until the pressure
 returns to baseline or an acceptable pressure is reported as determined by the study physician.
 Any changes in antihypertensive therapy will be recorded on the Concomitant Medication log and
 the event will be reported on the Adverse Event eCRF.
- The therapy pair or site physician shall remain available to participants via 24-hour cellular phone for integration, as needed.

At the end of each Experimental Session, the therapy pair (in consultation with site physician, if necessary) will assess the participant to decide if they are physically and emotionally stable. If the participant is not stable, the therapy pair and/or site physician will stay with the participant until stable or escalate for further care as appropriate.

Overnight Stay

If a participant is deemed medically and psychologically stable by the therapy pair at the end of the Experimental Session, the session will be ended and participant care transferred to the Night Attendant.

If a participant is deemed to be not psychologically stable at the end of the Experimental Session, they will remain under the care of their therapy pair. The therapy pair will continue to evaluate the participant to make further disposition recommendations depending on the participant's psychological condition. This could include: continued observation, psychological support and/or psychopharmacologic interventions; or further evaluation for potential transfer as appropriate per site Standard Operating Procedures (SOPs).

The following procedures will take place at overnight stays:

- Participants will remain overnight in an appropriately furnished room at or near the study site
 until after the Integrative Session the morning after each Experimental Session. With prior
 approval of the therapy pair, a companion may accompany the participant during the overnight
 stay.

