### **3.3 Safety Objectives**

The overall safety objective is to assess severity, incidence and frequency of Adverse Events (AEs), Treatment Emergent AEs (TEAEs), AEs of Special Interest (AESIs), and Serious Adverse Events (SAEs), concomitant medication use, suicidal ideation and behavior, and vital signs to support the package insert for MDMA-assisted therapy. The following safety objectives will evaluate the safety of MDMA-assisted therapy:

1. Assess incidence of AEs during Experimental Sessions that may be indicative of a medical complication of the Investigational Medicinal Product (IMP) such as clinical signs and symptoms of chest pain, shortness of breath, or neurological symptoms or any other signs or symptoms that prompt additional vital sign measurements
2. Assess incidence of AEs by severity
3. Assess incidence of TEAEs by severity
4. Assess incidence of TEAEs by severity reported during an Experimental Session, 1 day, and 2 days after IMP administration
5. Assess incidence of AESIs, defined as AEs specified in the protocol related to cardiac function, suicidality, and abuse liability
6. Assess incidence of AEs by severity categorized as leading to discontinuation of IMP, resulting in death or hospitalization, and continuing at Study Termination
7. Assess incidence of SAEs
8. Assess incidence of concomitant medications taken during an Experimental Session, 1 day, and 2 days after IMP administration
9. Assess incidence of psychiatric concomitant medications taken during the Treatment Period
10. Assess incidence of positive or serious suicidal ideation and positive suicidal behavior assessed with the Columbia Suicide Severity Rating Scale (C-SSRS)
11. Assess changes in blood pressure (BP), heart rate, and body temperature from pre-IMP administration to end of each Experimental Session

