Visit Timing	1 to 14 days after V3	Morning after V4	10 to 18 days after V4	At least 2 days after V6; 1 to 14 days before V8	21 to 56 days after V4	Morning after V8	10 to 18 days after V8	At least 2 days after V10; 1 to 14 days before V12	21 to 56 days after V8	Morning after V12	10 to 18 days after V12	At least two days after V14	24 to 32 days after V12
Past/Current Medication & Adherence	✓	✓	✓	✓	✓	✓	✓	✓	✓	✓	✓	✓	✓
Drug Screen	✓				✓				✓				
Pregnancy Screen	✓				✓				✓				
All AEs A	✓	✓	✓	✓	✓	✓	✓	✓	✓	✓	✓	✓	✓
Container Assignment B	✓				✓				✓				
Administer IMP	✓				✓				✓				
8-hour Exp. Session	✓				✓				✓				
BP, Pulse, Temperature	✓ C				✓ C				✓ C				✓ D
Potential Overnight Stay	✓				✓				✓				
90-min Integrative Session		✓	✓	✓		✓	✓	✓		✓	✓	✓	
Phone Call Follow-up E		✓				✓				✓			
Weight													✓
Blood Draw (CRP)													✓
Measures (ePRO or Clinician-Administered G )	✓	✓ E	✓	✓	✓	✓ E	✓	✓	✓	✓ E	✓	✓	✓

A All Adverse Events (AEs) includes collecting Serious Adverse Events, AEs of Special Interest, AEs of Psychiatric Status, AEs requiring medical advice or attention, AEs that indicate withdrawal of a participant, and all other AEs

B Obtain container assignment 24 to 48 hours prior to each Experimental Session

C During Experimental Sessions, vitals are measured before Investigational Product administration, immediately before the supplemental dose is administered (or would be, if supplemental dose not given), and approximately 8 hours after initial dose, and as needed

D At Study Termination, only blood pressure needs to be measured

E 14 days of phone call follow-up: every other day after the Experimental Session; includes C-SSRS administration and AE collection

F All Integrative Sessions must be at least 2 days apart

G Refer to [Table 6: Time and Events-Measures](#) for details

Visit Description	Visit #	Screening		Preparatory Period			Treatment 1				Treatment 2				Treatment 3				Study Termination
		Screening	IR Screening	V1	V2	V3	V4	V5	V6	V7	V8	V9	V10	V11	V12	V13	V14	V15	V16

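### The session-end vital-sign change in objective 11 has no fixed reading time and can be tied to elevations having resolved, so it tends to understate the acute effect, mainly after the supplemental dose

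*Protocol*

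**What the plan says.** SAP 3.3, item 11, gives the objective as "Assess changes in blood pressure (BP), heart rate, and body temperature from pre-IMP administration to end of each Experimental Session". Protocol 2.3 has the same item.

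On when a session ends, Protocol 7.3.1 (End of Experimental Session) says "The session may be ended if all medical and psychiatric parameters are acceptable". The same sentence adds that "elevations in vital signs have resolved to pre-IMP levels", with no numeric tolerance. The next bullet begins "Participants with persistent elevations in blood pressure at the end of Experimental Sessions will" and goes on to require further blood pressure readings after the session and the next morning.

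On when the late reading is taken:
- Protocol Table 5, footnote C: "approximately 6 hours after initial dose, and as needed".
- Protocol Table 7: 17:30, with the initial dose at 10:00.
- SAP Table 2, footnote C: "approximately 8 hours after initial dose, and as needed".

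On session length, Protocol 7.3.1 says "Experimental Sessions must be at least 6 hours long, measured from 30 minutes prior to IMP administration". SAP Table 2 still shows an 8-hour session.

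SAP 8.8.5 tabulates three time points: before dosing, before the supplemental dose, and session end. It adds change from Baseline without naming the time point or the baseline. SAP 8.4 takes Baseline resting blood pressure from Screening. Protocol Table 5, footnote C, also calls for extra readings when clinically indicated. SAP 8.0 sends data that the plan does not analyse to listings only.

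**The concern.** The moment at which objective 11 is measured can depend on the quantity being measured. If the end value is the reading that cleared the participant for release, it has been selected for showing no rise, while falls are not limited in the same way. If it is the scheduled late reading, it comes when the Protocol itself expects the effect to have largely gone. In both cases the session-end change is a poor measure of the acute effect of a sympathomimetic drug.

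The vital-sign objectives are meant to support the package insert, and Protocol 9.1 describes dose-dependent blood pressure rises whose characterisation in controlled hypertension is continuing. Protocol 4.6 expects the supplemental dose to add little beyond the initial peak. The only routine reading after that dose is the late one, so the planned tables can hardly test this expectation.

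**Working it through.** The documents give no expected vital-sign change and no power figure, so there is no stated number to reproduce. Two checks were made.

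**1. Timing.** Inputs: supplemental dose 1.5 to 2 h after the initial dose (Protocol 7.3.1); "peak effects occur 1.25 to 2 hours after the initial dose" (Protocol 1.2.2); cardiovascular changes usually over within 6 h (Protocol 9.1).

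- Table 7 late reading: 17:30 - 10:00 = 7.5 h after the initial dose, and 17:30 - 11:30 = 6.0 h after the supplemental dose.
- Late reading after the supplemental dose, over the three stated times: earliest 6 - 2 = 4 h; latest 8 - 1.5 = 6.5 h.
- Shortest permitted session: 6 - 0.5 = 5.5 h after dosing, half an hour before the 6 h reading. No reading is scheduled at 5.5 h; the point is only that the session may already be over when the 6 h reading is due.
- The reading before the supplemental dose, at 1.5 to 2 h, lies inside the stated peak window of the initial dose.
- If the supplemental dose has the same lag to peak (an assumption), its peak falls between 1.5 + 1.25 = 2.75 h and 2 + 2 = 4 h after the initial dose. No reading is scheduled in that interval.

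**2. Effect of a release rule on the mean.** Let X be the change a clock-timed reading would show, taken as normal with mean m and SD s. The values of m and s are assumptions. If release always waits until the change is no longer positive, the recorded value is min(X, 0), with mean

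E[min(X, 0)] = m·Φ(-m/s) - s·φ(m/s).

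For m = 5, s = 10: 5 × 0.3085 - 10 × 0.3521 = 1.54 - 3.52 = -1.98. If half of those with a raised reading are released anyway, the mean is 0.5 × 5 + 0.5 × (-1.98) = 1.51. Simulation with 400,000 draws per setting gave:

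| Assumed mean, SD (mmHg) | Share above zero on the clock | Mean, strict rule | Mean, half released anyway |
|---|---|---|---|
| 0, 10 | 0.50 | -4.0 | -2.0 |
| 0, 15 | 0.50 | -6.0 | -3.0 |
| 5, 10 | 0.69 | -2.0 | +1.5 |
| 5, 15 | 0.63 | -3.8 | +0.6 |
| 10, 10 | 0.84 | -0.8 | +4.6 |
| 10, 15 | 0.75 | -2.3 | +3.9 |

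A tolerance softens this. For mean 5 and SD 10, holding participants only until the change is at most 5 or 10 mmHg gives +1.0 or +3.0. The direction is the same throughout: a release reading understates the clock-timed value.

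**The case against.** A reader might infer that the rule forces the endpoint to zero or below, so that the drug would look inert whatever its real effect. The documents do not support that, for four reasons.

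- The wording is permissive: a session may be ended if the conditions hold. The next bullet provides for pressure still raised at the end, so some sessions are expected to close with an elevation.
- The late reading has clock times. A reading taken on the clock is not selected by resolution. The times disagree and the end value is undefined, but selection is a possibility and not a certainty.
- The tables are not confined to session end. The reading before the supplemental dose falls in the initial peak window and is summarised, so an acute rise would still be visible.
- With elevations usually over within 6 h, a reading at 6 to 8 h would tend toward pre-dose values with no release rule at all. Showing return to pre-dose is itself a legitimate safety summary.

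Clinically prompted readings are also not lost. They appear in listings, objective 1 covers adverse events that prompt extra measurements, and hypertensive crisis is an event of special interest.

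All of this stands, and it limits the point. It does not settle which reading is the end value, describe the period after the supplemental dose, or put the extra readings in a table.

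**Conclusion.** The concern holds in a limited form. Objective 11 rests on an end value that the documents do not define, at a time stated in three ways (about 6, 7.5 and about 8 h). Two bullets of Protocol 7.3.1 do not fit together on whether a session can end with a raised reading. The session-end change will tend to understate the acute effect, through selection if the release reading is used and through lateness if the scheduled one is. The understatement concerns the stated endpoint and the hours after the supplemental dose, where the only scheduled reading comes 4 to 6.5 h after that dose.

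The size cannot be derived from the documents. The mmHg figures illustrate direction under assumed means and SDs, and the strict column applies only if every session waits for full resolution. The change-from-Baseline table has a further ambiguity: objective 11 starts from the pre-dose reading of the session, whereas SAP 8.4 names the Screening blood pressure as Baseline.

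**What to change.** In objective 11 and SAP 8.8.5:

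1. Define the late value as the scheduled reading, report its recorded time since the initial and supplemental doses, and keep any release reading separate.
2. Report change from the same session's pre-dose value, not the Screening blood pressure, at both the pre-supplemental and the late reading.
3. Add the maximum observed post-dose change per participant per session over all scheduled and unscheduled readings, with number and percent above categories chosen by the sponsor. Show it beside the timed values, not in their place.
4. Count sessions in which an elevation persisted at session end.

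Reconcile the 6 h, 7.5 h and 8 h statements, the session length, and the two bullets in Protocol 7.3.1. Which session-ending rule is clinically right is for the sponsor and investigators to decide.

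The cost is SAP wording, reconciled Protocol text and a few derived variables from readings already taken. There are three drawbacks. The maximum rises with the number of readings, and symptomatic participants are measured more often, so it needs that caveat. It cannot fill the interval in which nothing is scheduled. The reported change may also look less favourable.

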7.3.2 Telephone Contact After Experimental Sessions

The goal of the telephone contact is to assess health changes, ensure participant safety, and offer support. The therapy pair will follow-up with the participant by telephone every other day for 14 days after each Experimental Session. If an Integrative Session falls on the date of a planned phone call, the phone call does not need to be performed. Each call will last on average 5 to 20 minutes but could be longer to address participant concerns and to adequately assess wellbeing. Additional telephone contact can be initiated at the request of the therapy pair or participant.

At each telephone contact, the therapy pair will:

- Inquire about any possible changes in health, assess the participant's mental health and the status of any previously recorded AEs, and record AEs as described in Section 10.0 Safety.
- Administer the Since Last Visit C-SSRS.
- Inquire about concomitant medication use and adherence.
- Offer support in accordance with the Treatment Manual.

7.3.3 Integrative Sessions

After each Experimental Session, three Integrative Sessions will take place. Each session will consist of 90 minutes of therapy. Integrative Sessions should not be less than 48 hours apart. The therapy pair may record the sessions. Integrative Sessions 1.2, 1.3, 2.2, 2.3, 3.2, and 3.3 may be performed via telemedicine.

MAPPUSX Protocol

Amendment 3 Version 1: 15 March 2023

Treatment 1

- Integrative Session 1.1 (Visit 5): morning after Experimental Session 1 (Visit 4).
- Integrative Session 1.2 (Visit 6): 10 to 18 days after Experimental Session 1 (Visit 4). The participant will complete the PCL-5 and LEC-5.
- Integrative Session 1.3 (Visit 7): at least 2 days after Integrative Session 1.2 (Visit 6) and 1 to 14 days in advance of Experimental Session 2 (Visit 8). This visit serves two purposes: to continue integration and to prepare for the next Experimental Session.

Treatment 2

- Integrative Session 2.1 (Visit 9): morning after Experimental Session 2 (Visit 8).
- Integrative Session 2.2 (Visit 10): 10 to 18 days after Experimental Session 2 (Visit 8). The participant will complete the PCL-5 and LEC-5.
- Integrative Session 2.3 (Visit 11): at least 2 days after Integrative Session 2.2 (Visit 10) and 1 to 14 days in advance of Experimental Session 3 (Visit 12). This visit serves two purposes: to continue integration and to prepare for the next Experimental Session.

Treatment 3

- Integrative Session 3.1 (Visit 13): morning after Experimental Session 3 (Visit 12).
- Integrative Session 3.2 (Visit 14): 10 to 18 days after Experimental Session 3 (Visit 12). The participant will complete the PCL-5 and LEC-5.
- Integrative Session 3.3 (Visit 15): at least 2 days after Integrative Session 3.2 (Visit 14).

During Integrative Sessions, the therapy pair will:

- Inquire about any possible changes in health. Assess the participant's mental health and the status of any previously recorded AEs. Record AEs as described in Section 10.0 Safety.
- Inquire about concomitant medication use and adherence.
- Administer Since Last Visit C-SSRS to determine suicidal risk.
- Discuss and review events that occurred with the participant during the Experimental Session, including thoughts, feelings, and memories. If necessary, the therapy pair will help the participant to reduce any residual psychological distress they are experiencing. The therapy pair will also encourage the transfer of states of acceptance, feelings of intimacy, closeness, and reduced fear experienced in Experimental Sessions to emotionally threatening everyday situations. The therapy pair will be supportive, validate the experience, and facilitate understanding and emotional clearing.
- Be accessible for additional support via phone or telemedicine if needed.
- At each second Integrative Session, participants will complete the LEC-5 and PCL-5, under the direction of the therapy pair, who will remind them of the index trauma listed in the parent study to which PTSD symptoms should be anchored.

